15. STATISTICAL METHODS

General considerations

Baseline variables will be summarized with appropriate descriptive statistics within each starting treatment group. Significance of any differences will be assessed using the Wilcoxon rank sum (non-normal data) or t-test for continuous data, and the chi-square test for categorical data.

15.1 Statistical Methods for Specific Aims

For **Specific Aim 1**, treatment group (sildenafil vs. placebo) is the *exposure* of interest, with vascular function measures: (1) percent increase in mean maximum brachial artery diameter (%BAD) using FMD (continuous), and (2) mean PAT ratio (continuous) using EndoPAT 2000, as the *primary outcomes* of interest (measured at 0, 3 months pre- and post-washout, and 6 months). Given the cross-over design, analyses will focus on within-subject comparisons of sildenafil versus placebo periods. All tests will be 2-sided with $\alpha=0.05$.

The analysis will use linear mixed models, with a term for treatment order (i.e. randomized initially to sildenafil or placebo), to assess whether %BAD and mean PAT ratio differ significantly between the sildenafil and placebo periods within subjects, adjusting for treatment order and CVD risk factors, baseline RA and CV medication use, disease activity (CDAI) and duration, and baseline levels of %BAD and PAT. Model fit, appropriate assumptions (e.g. normality, linearity, homoscedasticity), and potential collinearity, will be assessed with standard diagnostic plots and variance inflation factors (VIF). If needed, we will explore corresponding transformations of the covariates, and/or (in the case of collinearity) dropping variables from the model. We will address any non-compliance using an intention-to-treat strategy and will conduct a sensitivity analysis to conservatively assess observing how the worst outcome would affect results. We do not anticipate many will have RA medication changes but those participants will be included in the analysis; a secondary sensitivity analysis will add a covariate (at the corresponding time point(s)) to denote (yes or no) whether medication changed during the course of the study. Although we recognize that different types of medication changes may have

different effects on the outcome, we will not have sufficient power to estimate heterogeneity of effects across different types of medication changes.

Secondary outcomes of interest for Specific Aim 1 are the frequencies of AEs and SAE. Since the absolute numbers of these events is anticipated to be small, Fisher's exact tests will be used to compare these frequencies between the initial sildenafil and placebo groups.

For **Specific Aim 2**, treatment group is again the *exposure* of interest, with multiple continuous biomarkers of atherosclerosis as the *outcomes* of interest. Using the same analysis strategy as Specific Aim 1, linear mixed models will be used for each of these atherosclerosis biomarkers as functions of treatment group status, treatment order, clinically important covariates, and any significant baseline factors. Model fit and assumptions will again be checked via standard diagnostic plots and VIF.

To inform future trials, we will summarize differences in outcome measures from the beginning to end of the washout period, and compared to baseline, with mean (standard deviation) and median (range). P-values will be calculated with paired t-tests or Wilcoxon signed-rank tests for non-normal distributions.

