Methodology	
This study is designed to investigate the efficacy and safety of sildenafil 50 mg once daily in RA patients with no known history of CVD, but at least one traditional CV risk factor. Patients will be randomized 1:1 to receive either sildenafil or placebo for 3 months, then after a 2-week washout, crossed over to each respective group for an additional 3 months. Vascular studies validated in assessing endothelial dysfunction (brachial artery flow-mediated dilation [FMD]²⁻⁴ and peripheral arterial tone [PAT])⁵ and laboratory studies for selected atherosclerosis biomarkers will be performed at baseline, 3 months pre- and post-washout, and 6 months. Adverse events will be collected to assess sildenafil's safety.

Type of control	Placebo
Number of subjects	Up to 80 randomized subjects (to achieve final total of 60 subjects after expected ~20% drop-out)
Primary variable	Vascular function, determined through brachial arterial flow-mediated dilation (FMD) and peripheral arterial tone (PAT)
Plan for statistical analysis	
For the primary variable, treatment group (sildenafil vs. placebo) is the exposure of interest, with vascular function measures: (1) percent increase in mean maximum brachial artery diameter (%BAD) using FMD (continuous), and (2) mean PAT ratio (continuous) using EndoPAT 2000, as the primary outcomes of interest (measured at 0, 3 months pre- and post-washout, and 6 months). Given the cross-over design, analyses will focus on within-subject comparisons of sildenafil versus placebo periods. All tests will be 2-sided with $\alpha=0.05$. The analysis will use linear mixed models⁶, with a term for treatment order (i.e. randomized initially to sildenafil or placebo), to assess whether %BAD and mean PAT ratio differ significantly between the sildenafil and placebo periods within subjects, adjusting for treatment order and CVD risk factors, baseline RA and CV medication use, disease activity (CDAI) and duration, and baseline levels of %BAD and PAT. Secondary outcomes of interest for Specific Aim 1 are the frequencies of AEs and SAEs. Since the absolute numbers of these events is anticipated to be small, Fisher's exact tests will be used to compare these frequencies between the initial sildenafil and placebo groups.

List of abbreviations

ACE	angiotensin-converting enzyme
ACR	American College of Rheumatology
AE	adverse event
AIDS	acquired immunodeficiency syndrome

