5. STUDY OBJECTIVES

5.1 Primary endpoint

- Specific Aim 1: To determine whether sildenafil use in RA patients leads to improvement in parameters of vascular function; and to confirm its safety profile.

5.2 The Primary Efficacy Outcome measures will be:

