5.2.2 Peripheral Arterial Tone (PAT)

PAT measured by the EndoPAT 2000 device is a non-invasive method to assess endothelial function. It is a standardized, rapid, and easy to apply method, and has been found to correlate with multiple traditional CV risk factors and to be responsive to interventions. PAT is a validated alternative measure to brachial arterial FMD in assessing endothelial function, and is less operator-dependent than FMD. FMD directly measures the dilation capability of the large-conduit artery, whereas PAT measures flow response hyperemia, which is related to endothelial function of small arteries of microcirculation. PAT measures endothelium-mediated changes in vascular tone using bio-sensors placed on fingertips. Changes in arterial tone are elicited by creating a down-stream hyperemic response of the brachial artery from arm occlusion. Contra-lateral arm measurements are used to control for concurrent non-endothelial dependent changes in vascular tone. The semi-automatically calculated result is an index of endothelial function.

5.2.3 Safety Profile: Adverse Event Outcomes:

All adverse event (AE) and serious adverse event (SAE) data will be collected by separate study personnel from those collecting other outcomes; we will document AE and SAE diagnosis, date of onset and resolution, severity, whether it was unexpected or related to intervention; whether the blind was broken; and outcome. Specific AE data will include all common side effects of sildenafil as per Micromedex.

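### %BAD and PAT are both primary outcomes tested at 0.05, and the plan does not say what combination of results would meet Aim 1

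*Combined protocol and SAP*

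**What the plan says.** Aim 1, in section 5.1, is to determine whether sildenafil "leads to improvement in parameters of vascular function; and to confirm its safety profile". The plural is not explained further.

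The synopsis, section 12.1 and section 15.1 each put FMD (%BAD) and PAT side by side as primary, without ranking them. Section 15.1 and the synopsis then state "All tests will be 2-sided with" alpha 0.05. The linear mixed models are used "to assess whether %BAD and mean PAT ratio differ significantly between the sildenafil and placebo periods within subjects".

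Three statements favour %BAD:

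- Section 15.2 sizes the trial on %BAD alone.
- Section 15.4 explains that choice by the longer and wider validation of %BAD compared with PAT.
- Section 15.4 names %BAD as the outcome for the worst-case sensitivity analysis of missing data.

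None of these is a testing order, and none makes PAT secondary.

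The place of safety varies. Under the heading "5.2 The Primary Efficacy Outcome measures will be", section 5 lists FMD, PAT and then 5.2.3, "Safety Profile: Adverse Event Outcomes". Section 12.1 lists only FMD and PAT. Section 15.1 says "Secondary outcomes of interest for Specific Aim 1 are the frequencies of AEs and SAE", and the synopsis agrees with it.

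**The concern.** Two primary hypotheses are each tested at the full 5%, and the aim they serve could be met by one of them or only by both. Until that is fixed, the false-positive rate of the Aim 1 conclusion is not defined, and the choice could be made after the results are known.

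A split result is realistic. Section 5.2.2 says "FMD directly measures the dilation capability of the large-conduit artery, whereas PAT measures flow response hyperemia", so the two outcomes look at different parts of the circulation. Section 2.1.1 notes that risk factors and anti-TNF drugs act differently on small and large vessels. If one outcome is significant and the other is not, the plan gives no instruction on what to conclude.

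**Working it through.** **1. The plan's own figure.** Inputs from section 15.2: n = 60, effect size d = 0.37, paired t-test. Section 15.1 gives two-sided alpha 0.05.

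- Noncentrality: d × √n = 0.37 × √60 = 2.866, with 59 degrees of freedom and critical value 2.001.
- Power from the noncentral t: 80.5%. The smallest n reaching 80% is 60.

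The stated 80% reproduces. The sample-size arithmetic is not in question.

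**2. Error rate if either outcome may meet Aim 1.** With no effect on either outcome and independent tests, P(at least one p < 0.05) = 1 − 0.95² = 9.75%. For correlated tests, P = 1 − P(|Z1| < 1.96 and |Z2| < 1.96) under a bivariate normal. The documents give no correlation between the two test statistics, so a range is shown:

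| Assumed correlation | Chance of at least one false positive |
|---|---|
| 0 | 9.75% |
| 0.3 | 9.5% |
| 0.5 | 9.1% |
| 0.7 | 8.3% |
| 0.9 | 7.0% |

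These figures count a significant difference in either direction, as the plan's own 5% does. Counting only false findings of improvement, the independent case is 1 − 0.975² = 4.9% against a nominal 2.5%, so the doubling is the same.

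**3. Error rate under the other readings.** If both must be significant, the chance of a false Aim 1 conclusion is at most 5%, because at least one true null must be rejected at 5%. If each outcome supports only its own separate claim, each claim carries its own 5%.

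**4. What each possible rule costs.** All figures use the paired t-test at d = 0.37 for %BAD. Section 15.2 itself says that power under the final mixed model is hard to estimate.

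- *Fixed sequence, %BAD first.* %BAD is tested at 0.05, so power stays at 80.5% with n = 60. PAT is reached only after %BAD is rejected, which holds the family-wise error at 5%.
- *Both required.* Joint power is about 65% at correlation 0 (0.805² = 0.648), 69% at 0.5 and 76% at 0.9. This assumes that PAT also has effect size 0.37; the documents give no effect size for PAT.
- *Equal split, 0.025 each.* Critical value 2.300; power for %BAD falls to 71.3% at n = 60. The effect detectable with 80% power rises from 0.368 to 0.407. Holding 80% power at d = 0.37 needs 72 evaluable subjects. At the synopsis's drop-out of about 20%, that is 72 / 0.8 = 90 randomized, against a ceiling of 80.

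**The case against.** The strongest reply is that no inflation has been shown. The documents never say that success on either outcome is enough. Section 15.1 numbers the outcomes separately and section 5.2.2 assigns them to different vessels, so reporting each on its own terms is a natural reading. This is also a single-center phase II trial, where strict control is less often demanded. This stands in part: the inflation is conditional, and what the text shows is an unstated decision rule. But the synopsis calls this an efficacy trial, names primary outcomes, fixes alpha and powers a hypothesis test. A reader is entitled to know which result answers the aim.

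A second reply is that section 15.4 already makes %BAD the lead outcome. It does lean that way, and on more than sizing, since it also names %BAD for the worst-case analysis and cites its longer validation. It still sets no order, while the synopsis, 12.1 and 15.1 keep PAT as a co-equal primary.

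A third reply is that a fixed sequence changes the standing of PAT and so is more than a wording matter. That is correct, and it is the real cost of the proposal.

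Two stronger readings are tempting. A reader might infer that the trial runs at a false-positive rate near 10%; that holds only under an either-outcome rule, which the documents leave open. A reader might also take the listing of safety under the primary efficacy heading in 5.2 as a third primary test. The synopsis and 15.1 both make adverse events secondary, so this is an editorial mismatch and adds nothing to the efficacy multiplicity.

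**Conclusion.** The point holds as a gap in the decision rule. Two unranked primary outcomes are each tested at two-sided 0.05, and the text available does not say what would meet Aim 1. The text between sections 5.3 and 7 was not available and could not be checked.

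The consequence depends on the reading: 7.0% to 9.75% for at least one false positive if either outcome counts, over assumed correlations from 0.9 down to 0, and no inflation if both are required or the claims are kept separate. The planned sample size is unaffected. This is a cheap improvement worth making, not a flaw that invalidates the design.

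**What to change.** In section 15.1 and the synopsis, state that:

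- %BAD is tested first at two-sided 0.05.
- PAT is tested at two-sided 0.05 only if %BAD is significant.
- The Aim 1 efficacy conclusion rests on %BAD.

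This follows the preference already expressed in 15.2 and 15.4. If the sponsor wants PAT to keep equal standing, requiring both or splitting alpha also controls the error, at the power costs shown above. Whichever rule is chosen should be written down.

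Date the amendment before database lock. Section 9.4 says the data stay blinded until then, but section 16.4 gives the data manager and study statistician access to treatment assignment. The amendment should therefore also record that the choice was made by people who had not seen outcome data by treatment.

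In the same amendment, make the place of safety agree between 5.2.3, 12.1, 15.1 and the synopsis, and check the result against the registered outcomes, since section 16.3 says the trial is registered.

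The cost is a protocol amendment and no extra patients. The downside is that a significant PAT result with a non-significant %BAD result could be reported only as exploratory.

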7.3 Phase two

7.3.1 Initial Study Treatment phase (Month 0 to Month 3)

Once Screening is fully satisfied, participants will proceed to the Baseline visit. At the Baseline study staff will dispense Study Drug.

Note: Screening and baseline can occur on the same day if clinical labs (creatinine and LFTs) have been drawn as part of routine care within 3 months of the baseline.

Participants will begin use of study drug the day after baseline visit and will remain on that regimen (changes notwithstanding) for 3 months (+/- 7 days).

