10. STUDY PROCEDURES

10.1 Timing of procedures

Screening and baseline visits can occur on the same day.

- Visit Windows

There are windows of time specific to any given visit in which the visit may take place without deviating from the protocol by being “Late” or “Early”.

- Baseline Visit must occur within 28 days of Screening, otherwise, Screening must be repeated.
- Three Month Visit must occur three months +/- 7 days after Baseline
- The Two Week Washout Visit must take place between fourteen and seventeen days after Three Month Visit
- Six Month Visit must occur three months +/- 7 days after the Two Week Washout Visit

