14. SAFETY

14.1 Definition of adverse event (AE)

In a clinical study, an AE is any untoward medical occurrence (i.e., any unfavorable and unintended sign [including abnormal laboratory findings], symptom or disease) in a patient or clinical investigation subject after providing written informed consent for participation in the study. Therefore, an AE may or may not be temporally or causally associated with the use of a medicinal (investigational) product.

In the following differentiation between medical history and AEs, the term “condition” may include abnormal e.g., physical examination findings, symptoms, diseases, laboratory, ECG.

- Conditions that started before signing of informed consent and for which no symptoms or treatment are present until signing of informed consent will be recorded as medical history (e.g., seasonal allergy without acute complaints).
- Conditions that started before signing of informed consent and for which symptoms or treatment are present after signing of informed consent, at *unchanged intensity*, will be recorded as medical history (e.g., allergic pollinosis).
- Conditions that started or deteriorated after signing of informed consent will be documented as AEs.

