14.8 Serious Adverse Events

14.8.1 Reporting

- Sponsor

Pfizer is the provider of the study drug Sildenafil and its placebo ("drug sponsor"). Serious Adverse Events must be reported to the drug sponsor utilizing the forms provided by Pfizer and in accordance with the guide they have provided. These items can be found in the Manual of Operations and Procedures (MOOP) under Safety Reporting.

- Independent Safety Officer

Investigator’s notification to the Independent Safety Officer

All SAEs occurring during the observation period defined in Section 14.8 must immediately (within 48 hours of the investigator’s awareness) be reported to KAI, NIAMS and the independent Safety Officer. An SAE form must also be completed within 48 hours of the investigator awareness and forwarded. Each SAE must be followed up until resolution or stabilization by submission of updated reports.

- IRB

Notification of the IRB

Notification of the University of Pittsburgh IRB about all relevant events (e.g., SAEs, suspected, unexpected, serious adverse reactions [SUSARs]) will be performed according to IRB regulations.

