15.2 Sample Size Justification

We aim to recruit up to 80 subjects to achieve a final sample size of 60 evaluable subjects. For Aim 1, the **sample size of 60** (30 in initial sildenafil group and 30 in initial placebo group), gives 80% power for a relatively small effect size of 0.37 for the change in %BAD in the sildenafil versus placebo periods (using a paired t-test, although we will use a linear mixed model for the analysis). Based on previous studies in diabetes, with equivalent CV risk, the estimated standard deviation (SD) of %BAD is approximately 4. The effect size of 0.37 thus corresponds to a % increase of 1.5%, which is clinically meaningful. We will analyze drop-ins, drop-outs, withdrawals, and non-adherences according to intention-to-treat principles.

For Aim 2, given that we are using the same analysis strategy as Aim 1, the sample size of 60 (30 in each group) again yields 80% power to detect an effect size of 0.37 for the change in a given biomarker. The estimated power (in either aim) corresponding to the final mixed model is difficult to estimate more

specifically since it is unclear how much residual variability will remain after adjusting for other covariates, and/or whether a stronger association will be evident after model adjustment.

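### The only planned AE/SAE test compares initially assigned groups with no analysis window or period-of-onset rule: a whole-trial count would nearly cancel a drug effect, and a period-1 count is valid but omits period 2

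*Combined protocol and SAP*

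**What the plan says.** Section 15.1 and the synopsis (Section 1) class AE and SAE frequencies as secondary outcomes of Specific Aim 1 and give them one analysis: Fisher's "exact tests will be used to compare these frequencies between the initial sildenafil and placebo groups". No power or sample size is stated for it.

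The design is a two-period crossover. Section 7.1 has every participant take both treatments, three months each, and gives as one advantage that up to 80 recruited participants can contribute safety data.

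Data collection is well described. Under Section 14.1, "Conditions that started or deteriorated after signing of informed consent will be documented as AEs". Section 5.2.3 records "date of onset and resolution, severity, whether it was unexpected or related to intervention", and Section 14.6 adds a clinical judgement of relatedness. AEs are recorded at Visits 2 to 5 (Sections 10.2.2 to 10.2.5). Collection therefore spans some pre-dose time ("Baseline Visit must occur within 28 days of Screening") and the washout ("The Two Week Washout Visit must take place between fourteen and seventeen days after Three Month Visit").

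Nothing says which of these events enter Fisher's test, or to which treatment an event belongs. The word 'initial' does not settle it:

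- Section 7.3.1 is headed "Initial Study Treatment phase (Month 0 to Month 3"), which points to period 1.
- Section 15.2 describes the 60 evaluable participants as "30 in initial sildenafil group and 30 in initial placebo group", which is treatment order.
- Section 15.1 defines treatment order by the treatment to which a participant was first randomised, and Section 15.4 uses 'initial' in the same sense when discussing medication changes over six months.

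**The concern.** In a crossover, a group defined by initial assignment is a sequence group. By the end of the trial both sequences have had the same two exposures in opposite order. A table of participants with any event, split by sequence and counted over the whole trial, therefore does not compare sildenafil with placebo. An analyst following Section 15.1 literally could produce that table, find similar percentages, and report no difference in headache or flushing when a real excess exists. Confirming the safety profile is part of the primary objective (synopsis and Section 5.1), so such a result would be read as reassurance.

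Limiting the count to period 1 gives a proper randomised comparison. The cost is that the test ignores everything after the washout, including all sildenafil exposure in the placebo-first group. It then uses neither the safety data that Section 7.1 expects the crossover to yield nor the within-subject comparison on which Section 15.1 says the analyses will focus.

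**Working it through.** **The plan's own figure.** The only stated power is for %BAD: 60 participants, effect size 0.37, paired t-test, 80%. The noncentral t (59 df, noncentrality 0.37 × √60) gives 80.5%, so it reproduces. There is no corresponding figure for AEs to check.

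**Inputs**
- Headache risk per 3-month period: pS = 0.21 on sildenafil and pP = 0.07 on placebo (Section 15.3.4, erectile-dysfunction participants at 50 mg daily). Section 14.9 gives 16% vs 4% for headache and 10% vs 1% for flushing.
- 40 per group: up to 80 randomised 1:1.
- Fraction d lost before period 2: 0, 0.20 (the synopsis figure), or 1 − 60/80 = 0.25 (implied by 80 randomised and 60 evaluable).
- Two-sided α = 0.05; unit of analysis is the participant with at least one event.
- Assumed: no period or carry-over effect, independent periods, drop-out unrelated to the event, and drop-outs contributing period 1 only.

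**Whole-trial count.** A completer in either sequence has risk

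w = 1 − (1 − pS)(1 − pP) = 1 − 0.79 × 0.93 = 0.265.

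With drop-out, the sildenafil-first risk is (1 − d)w + d·pS and the placebo-first risk is (1 − d)w + d·pP. The difference is d(pS − pP), so only the drop-out fraction of the true 14 points survives. Rejection rates are from exact enumeration.

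| d | Sildenafil first | Placebo first | Difference | Fisher rejection |
|---|---|---|---|---|
| 0 | 26.5% | 26.5% | 0 | 2.9% |
| 0.20 | 25.4% | 22.6% | 0.20 × 14 = 2.8 points | 3.5% |
| 0.25 | 25.2% | 21.7% | 0.25 × 14 = 3.5 points | 3.9% |

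The cancellation among completers follows from the design and holds at any pair of rates. Independence between periods affects only the level, 26.5%.

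**Period-1 count.** Exact Fisher power with 40 per group is 33.4% for headache at 21% vs 7%, 27.8% at 16% vs 4%, and 15.0% for flushing at 10% vs 1%.

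**What period 2 would add.** At 25% drop-out, participants exposed to each drug rise from 40 to 40 + 30 = 70.
- A period-adjusted GEE risk difference with a small-sample robust SE was simulated (80 randomised, 25% drop-out, 3,000 runs per scenario). For headache at 21% vs 7% it has 67% power if a person's responses in the two periods are independent, and 76% if half of placebo reactors also react on drug. The 95% CI half-width is 11.6 and 10.6 points respectively.
- A robust risk-difference test of the same kind on period 1 alone has 44-45% power and a half-width of 15.2 points.
- As a check that does not depend on the GEE, exact McNemar in 60 completers has 51% power at within-subject correlation 0 and 66% at 0.3.

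**The case against.** The strongest reply is that the plan means period 1. Fisher's test needs independent groups, Section 7.3.1 uses the word 'initial' for Months 0 to 3, and all randomised and treated participants would contribute. Read that way the test is sound, and what remains is a matter of precision for a secondary outcome with no power target and few expected events. This largely stands. It does not remove the ambiguity, because Sections 15.1, 15.2 and 15.4 use the word for treatment order and no section limits the count to period 1.

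It is also fair that leaving period 2 out of one test does not mean that period-2 events will go untabulated; the plan simply does not say. Relatedness is recorded, but a clinical judgement about each event is not a counting rule for the test.

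Three stronger readings are tempting and not supported.

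- A reader might infer that the plan specifies an invalid safety test. The documents show an unstated choice between two counts, one of which is valid.
- A reader might add the longest screening interval to the longest washout and conclude that much of the AE follow-up is off drug. That stacks two maxima. Section 10.1 lets screening and baseline fall on the same day, and pre-baseline events precede randomisation, so they add noise but favour neither group in expectation. Washout events are the part that needs a rule.
- Section 14.8.1 begins "All SAEs occurring during the observation period defined in Section 14.8 must immediately", and no such period appears in Section 14.8. A reader might take this as further evidence of a missing analysis window. It concerns SAE reporting, not this comparison.

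Finally, a two-period model should not automatically displace the randomised period-1 comparison. Section 8.4 withdraws participants who do not tolerate the drug, so period 2 is a selected set. In simulation the GEE difference averaged 14.8 points against a true 14.0 when 75% of sildenafil-first reactors left and responses were correlated. At 10% vs 1% its 95% CI coverage was 93-94%. This is why the two-period estimate belongs beside the period-1 test rather than above it.

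**Conclusion.** The concern holds as an ambiguity that should be closed, not as a demonstrated error. What is missing is an analysis window and a rule attributing events to the treatment period of onset; the collection window and onset dates already exist.

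Under a whole-trial count, only 0-25% of a true drug effect would appear in the comparison at 0-25% drop-out, and the test would reject 2.9-3.9% of the time in the headache example. Under a period-1 count the test is valid, with about 33% power in that example, but it leaves out all of period 2.

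The near-cancellation rests on the crossover itself and on there being no period or carry-over effect. The percentages are illustrative: they come from erectile-dysfunction populations, and the Section 14.9 table from as-needed, flexible dosing. The plan set no AE power target that these figures could fail. If period 1 was always intended, one sentence removes the serious risk; attribution by onset date remains worthwhile because it uses data that the trial already collects.

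**What to change.** Before unblinding, amend Section 15.1 and the synopsis to:

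1. Limit Fisher's test explicitly to events with onset from first dose to the end of period 1, and define that end point.
2. Assign every AE and SAE by onset date to the treatment period in which it began, with a stated rule for washout events, and list pre-dose events separately.
3. Tabulate participants with at least one event, and exposure time, on sildenafil and on placebo across both periods, for everyone who received each treatment.
4. For common AEs, add a by-treatment risk difference with 95% CI using both periods, alongside the period-1 test. A period-adjusted GEE with a small-sample robust SE would serve, as would a paired analysis in completers. Keep SAEs and sparse categories descriptive.

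Items 1 to 3 are the essential repair; the choice of estimator in item 4 is open. The cost is SAP wording and modest programming, with no new data or visits. The two-period estimate relies on the washout, which Section 7.1 already treats as adequate, and can be slightly affected by AE-driven withdrawal; the report should say so.
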